16.7 Financing and Insurance

Financing and Insurance are addressed separately in the Clinical Study Agreement.

16.8 Publication Policy

The publications policy is also provided in the Clinical Study Agreement. The data from this study will be available to the Investigators for publication upon the completion of the study. The Sponsor agrees to have the results published, whether positive or negative. A publication committee will be formed composed of the Investigators. The Sponsor will review any manuscripts to ensure that proprietary information has the appropriate patent protection prior to journal submission.

18.0 APPENDICES

Appendix 1 Schedule of Assessments

Appendix 2 Schedule of Laboratory Assessments

Appendix 3 CFQ-R, Adult Version (English)

APPENDIX 1: SCHEDULE OF ASSESSMENTS

Table A.1-1: Single Ascending Dose Cohorts 1-4

| Study Procedures | Screening | Check-In | | | | Discharge | | | | End of Study |
|----------------------------------------|-----------------------|----------------|----------------|----|----|-----------|----|-----|-----|----------------|
| Study Day | ≤14 days ^a | -1 | 1 ^b | 2 | 3 | 4 | 5 | 6 | 7 | 8 |
| In Hours | | -24 | 0 | 24 | 48 | 72 | 96 | 120 | 144 | 168 |
| Informed consent | X | | | | | | | | | |
| Demographics | X | | | | | | | | | |
| Medical History | X | | | | | | | | | |
| Eligibility Review | X | X | | | | | | | | |
| Concomitant Medications | X | X | X | X | X | X | | | | X |
| Adverse Events | | X | X | X | X | X | | | | X |
| Physical Exam | C | C | S | S | | S | | | | C |
| Height & Weight | H/W | W | W | | | | | | | W |
| Vital Signs ^c & Oximetry | X | X | X | X | X | X | | | | X |
| Spirometry ^d | X | X | X | X | | X | | | | X |
| Chest Xray | X ^e | | | | | | | | | X ^f |
| 12-lead ECG | X | | | | | | | | | X |
| 24-Hour Telemetry | | | X | | | | | | | |
| Blood for Safety Labs ^g | X | X ^h | X | X | X | X | | | | X |
| Urinalysis ^g | U | U ^h | U | U | U | U | | | | U |
| Drug Screen ^g | X | | | | | | | | | |
| Pregnancy Test ^{g,i} | X | X | | | | | | | | X |
| Sputum for Microbiology ^g | | X | | | | | | | | X |
| Blood for CFTR ^g | Genotyping | Sequencing | | | | | | | | |
| Biomarkers ^g | X | X | | X | | X | | | | X |
| Sweat Chloride ^g | X | | | | | | | | | |
| Randomization | | X | | | | | | | | |
| Study Drug Administration ^j | | | X | | | | | | | |
| Collect Samples for PK ^g | | | X | X | X | X | | | | X |

Abbreviations: C = complete physical exam; H = height; S = symptom-directed physical exam; U = urinalysis (dipstick); W = weight

^a The screening period for an individual subject may be extended for an additional 7 days at the discretion of the Sponsor's Medical Monitor. See Section 7.2 for details.

^b See Section 7.3.2 for details on timing of these assessments relative to study drug administration on Day 1.

^c Includes blood pressure, heart rate, respiratory rate, and temperature.

^d Includes FEV₁, FVC, and FEF₂₅₋₇₅.

^e A Chest Xray or CT scan obtained within 90 days of screening is acceptable if there was no intercurrent pulmonary illness during the interim.

^f Only subjects who experience pulmonary AEs during the study.

^g See Appendix 2 for a detailed schedule of these assessments, broken down by type of specimen and time relative to dose.

^h Only laboratory assessments that are abnormal (but not clinically significant) at screening should be repeated at Day-1.

ⁱ Pregnancy test (preferably serum but urine is accepted) required for women of childbearing potential only.

^j Subjects who are taking concurrent CF therapy should receive this therapy prior to study drug dosing in the order specified in Section 6.3.1.

Table A.1-2: Multiple Ascending Dose Cohorts 5-8, WEEK 1

Dosing Schedule assumes Monday-Wednesday-Friday dosing:

| Study Procedures | Screening | | Dose 1 | Dose 2 | | Dose 3 | | |
|----------------------------------------|------------------------|----------------|--------|--------|----|--------|-----|-----|
| Study Day | ≤-14 days ^a | -1 | 1 | 3 | 4 | 5 | 6 | 7 |
| In Hours Post Dose 1 | | -24 | 0 | 48 | 72 | 96 | 120 | 144 |
| Informed consent | X | | | | | | | |
| Demographics | X | | | | | | | |
| Medical History | X | | | | | | | |
| Eligibility Review | X | X | | | | | | |
| Concomitant Medications | X | X | X | X | X | X | | |
| Adverse Events | | X | X | X | X | X | | |
| Physical Exam | C | C | S | S | S | S | | |
| Height & Weight | H/W | W | W | | | | | |
| Vital Signs ^b & Oximetry | X | X | X | X | X | X | | |
| Spirometry ^c | X | X | X | X | X | X | | |
| Chest Xray | X ^d | | | | | | | |
| 12-lead ECG | X | | | | | | | |
| Telemetry | | | X | | | | | |
| CFQ-R RSS ^e | | | X | | | | | |
| Blood for Safety Labs ^f | X | X ^g | X | X | X | | | |
| Urinalysis ^f | U | U ^g | U | U | U | | | |
| Drug Screen ^f | X | | | | | | | |
| Pregnancy Test ^{f,h} | X | X | | | | | | |
| Sputum for Microbiology ^f | | X | | | | | | |
| Blood for CFTR ^f | Genotyping | Sequencing | | | | | | |
| Biomarkers ^f | X | X | | | X | | | |
| Sweat Chloride ^f | X | | | | | | | |
| Randomization | | X | | | | | | |
| Study Drug Administration ⁱ | | | X | X | | X | | |

| Study Procedures | Screening | | Dose 1 | Dose 2 | | Dose 3 | | |
|-------------------------------------|-----------|--|--------|--------|---|--------|--|--|
| Collect Samples for PK ^f | | | X | X | X | X | | |

Abbreviations: C = complete physical exam; CFQ-R RSS = Cystic Fibrosis Questionnaire-Revised Respiratory Symptom Score; ECG = electrocardiogram; H = height; PK = pharmacokinetic; S = symptom-directed physical exam; U = urinalysis (dipstick); W = weight

NOTE: See also Section 7.4 for details on timing of assessments relative to study drug administration.

^a The screening period for an individual subject may be extended for an additional 7 days at the discretion of the Sponsor’s Medical Monitor. See Section 7.2 for details.

^b Includes blood pressure, heart rate, respiratory rate, and temperature.

^c Includes FEV₁, FVC, and FEF₂₅₋₇₅.

^d A Chest Xray or CT scan obtained within 90 days of screening is acceptable if there was no intercurrent pulmonary illness during the interim.

^e Should be completed prior to any other procedures or assessments.

^f See Appendix 2 for a detailed schedule of these assessments, broken down by type of specimen and time relative to dose.

^g Only laboratory assessments that are abnormal (but not clinically significant) at screening should be repeated at Day-1.

^h Pregnancy test (preferably serum but urine is accepted) required for women of childbearing potential only.

ⁱ Subjects who are taking concurrent CF therapy should receive this therapy prior to study drug dosing in the order specified in Section 6.3.1.

Table A.1-3: Multiple Ascending Dose Cohorts 5-8, WEEK 2

| Study Procedures | Dose 4 | | Dose 5 | | Dose 6 | | |
|----------------------------------------|--------|-----|--------|-----|--------|-----|-----|
| Study Day | 8 | 9 | 10 | 11 | 12 | 13 | 14 |
| In Hours Post Dose 1 | 168 | 192 | 216 | 240 | 264 | 288 | 312 |
| Concomitant Medications | X | | X | | X | | |
| Adverse Events | X | | X | | X | | |
| Physical Exam | C/S | | S | | S | | |
| Height & Weight | W | | | | | | |
| Vital Signs ^a & Oximetry | X | | X | | X | | |
| Spirometry ^b | X | | | | | | |
| Blood for Safety Labs ^c | X | | | | | | |
| Urinalysis ^c | U | | | | | | |
| Biomarkers ^c | X | | | | | | |
| Study Drug Administration ^d | X | | X | | X | | |
| Collect Samples for PK ^c | X | | X | | X | | |

Abbreviations: C = complete physical exam; PK = pharmacokinetic; S = symptom-directed physical exam; U = urinalysis (dipstick); W = weight

NOTE: See also Section 7.4 for details on timing of assessments relative to study drug administration.

^a Includes blood pressure, heart rate, respiratory rate, and temperature.

^b Includes FEV₁, FVC, and FEF₂₅₋₇₅.

^c See Appendix 2 for a detailed schedule of these assessments, broken down by type of specimen and time relative to dose.

^d Subjects who are taking concurrent CF therapy should receive this therapy prior to study drug dosing in the order specified in Section 6.3.1.

Table A.1-4: Multiple Ascending Dose Cohorts 5-8, WEEK 3

| Study Procedures | Dose 7 | | Dose 8 | | Dose 9 | | |
|----------------------------------------|--------|-----|--------|-----|--------|-----|-----|
| Study Day | 15 | 16 | 17 | 18 | 19 | 20 | 21 |
| In Hours Post Dose 1 | 336 | 360 | 384 | 408 | 432 | 456 | 480 |
| Concomitant Medications | X | | X | | X | | |
| Adverse Events | X | | X | | X | | |
| Physical Exam | C/S | | S | | S | | |
| Height & Weight | W | | | | | | |
| Vital Signs ^a & Oximetry | X | | X | | X | | |
| Spirometry ^b | X | | | | | | |
| CFQ-R RSS ^c | X | | | | | | |
| Blood for Safety Labs ^d | X | | | | | | |
| Urinalysis ^d | U | | | | | | |
| Biomarkers ^d | X | | | | | | |
| Study Drug Administration ^e | X | | X | | X | | |
| Collect Samples for PK ^d | X | | X | | X | | |

Abbreviations: C = complete physical exam; CFQ-R RSS = Cystic Fibrosis Questionnaire-Revised Respiratory Symptom Score; PK = pharmacokinetic; S = symptom-directed physical exam; U = urinalysis (dipstick); W = weight

NOTE: See also Section 7.4 for details on timing of assessments relative to study drug administration.

^a Includes blood pressure, heart rate, respiratory rate, and temperature.

^b Includes FEV₁, FVC, and FEF₂₅₋₇₅.

^c Should be completed prior to any other procedures or assessments.

^d See Appendix 2 for a detailed schedule of these assessments, broken down by type of specimen and time relative to dose.

^e Subjects who are taking concurrent CF therapy should receive this therapy prior to study drug dosing in the order specified in Section 6.3.1.

Table A.1-5: Multiple Ascending Dose Cohorts 5-8, WEEK 4

| Study Procedures | Dose 10 | | Dose 11 | | Dose 12 |
|--------------------------------------------------|---------|-----|---------|-----|---------|
| Study Day | 22 | 23 | 24 | 25 | 26 |
| In Hours Post Dose 1 | 504 | 528 | 552 | 576 | 600 |
| Concomitant Medications | X | | X | | X |
| Adverse Events | X | | X | | X |
| Physical Exam ^a | C/S | | S | | C/S |
| Height & Weight | W | | | | W |
| Vital Signs ^b & Oximetry ^a | X | | X | | X |
| Spirometry ^{a,c} | X | | | | X |
| Blood for Safety Labs ^d | X | | | | |
| Urinalysis ^d | U | | | | |
| Biomarkers ^d | X | | | | |
| Sweat Chloride ^d | | | | | X |
| Study Drug Administration ^e | X | | X | | X |
| Collect Samples for PK ^d | X | | X | | X |

Abbreviations: C = complete physical exam; PK = pharmacokinetic;

S = symptom-directed physical exam; U = urinalysis (dipstick); W = weight

^a See Section 7.4 for details on timing of these assessments relative to study drug administration.

^b Includes blood pressure, heart rate, respiratory rate, and temperature.

^c Includes FEV₁, FVC, and FEF₂₅₋₇₅.

^d See Appendix 2 for a detailed schedule of these assessments, broken down by type of specimen and time relative to dose.

^e Subjects who are taking concurrent CF therapy should receive this therapy prior to study drug dosing in the order specified in Section 6.3.1.

Table A.1-6: Multiple Ascending Dose Cohorts 5-8, Follow-Up Visits

| Study Procedures | PK Follow-up 24 Hours After Last Dose | PK Follow-up 96 Hours After Last Dose | 7 Days After Last Dose (End of Treatment) | Follow-up 28 Days after Last Dose (End of Study) |
|--------------------------------------|---------------------------------------------|---------------------------------------------|----------------------------------------------------|-----------------------------------------------------------|
| Study Day | 27 ± 1 | 30 ± 2 | 33 | 54 |
| In Hours Post Dose 1 | 624 ± 12 | 696 ± 48 | 768 | 1272 |
| Concomitant Medications | | | X | X |
| Adverse Events | | | X | X |
| Physical Exam | | | C | C |
| Height & Weight | | | W | W |
| Vital Signs ^a & Oximetry | | | X | X |
| Spirometry ^b | | | X | X |
| Chest Xray | | | X | |
| 12-lead ECG | | | X | |
| CFQ-R RSS ^c | | | X | X |
| Blood for Safety Labs ^d | | | X | X |
| Urinalysis ^d | | | U | U |
| Pregnancy test ^{d,e} | | | X | X |
| Sputum for Microbiology ^d | | | X | |
| Biomarkers ^d | | | X | X |
| Sweat Chloride ^d | | | X | X |
| Collect Samples for PK ^d | X | X | X | X |

Abbreviations: C = complete physical exam; CFQ-R RSS = Cystic Fibrosis Questionnaire-Revised Respiratory Symptom Score; PK = pharmacokinetic; U = urinalysis (dipstick); W = weight

^a Includes blood pressure, heart rate, respiratory rate, and temperature.

^b Includes FEV₁, FVC, and FEF₂₅₋₇₅.

^c Should be completed prior to any other procedures or assessments.

^d See Appendix 2 for a detailed schedule of these assessments, broken down by type of specimen and time relative to dose.

^e Pregnancy test (preferably serum but urine is accepted) required for women of child-bearing potential only.

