4.0 STUDY OVERVIEW

4.1 Criteria for Evaluation

4.1.1 Primary Endpoint

- Incidence and severity of adverse events (AEs) from baseline through end of study
- Occurrence of dose-limiting toxicities (DLT) in each dose cohort from baseline through end of study

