7.4.9 Week 4 (Dose 12)

Pre-dose:

1. Complete physical examination (including body weight)
2. Vital signs
3. Oximetry
4. Concomitant medications review
5. AE review
6. Obtain blood and urine samples for PK prior to dosing
7. Administer any routine pulmonary medications and airway clearance techniques, including SABA and/or LABA, Pulmozyme, inhaled corticosteroids and/or antibiotics
8. Spirometry (FEV₁, FVC, and FEF₂₅₋₇₅)
9. Administer study drug

Post-dose:

1. Symptom-directed physical examination within 2 hours post dose
2. Vital signs within 2 hours post dose
3. Oximetry within 2 hours post dose
4. Spirometry at 20, and 60 minutes, 4 hours post dose
5. Obtain the following samples for PK:
 - Blood at 1, 2, 3, 4, and 8 hours post dose
6. Obtain sample for sweat chloride determination

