7.4.10 Follow-up Visit for PK—24 hours +/- 12 hours After Last Dose

Subject to return to clinic to obtain serum and urine samples for PK. The samples can be collected any time within the time window specified.

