12.4.2 Eliciting Adverse Events

A consistent methodology of non-directive questioning for eliciting AEs at all subject evaluation time points should be adopted. Examples of non-directive questions include:

“How have you felt since your last clinic visit?”

“Have you had any new or changed health problems since you were last here?”

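### After dose 12 the next scheduled AE and concomitant-medication review is 7 days away, longer than after any earlier dose, although the subject is back in clinic twice for PK

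*Protocol*

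**What the plan says.** - **Follow-up schedule.** Protocol Table A.1-6 sets the visit days as "Study Day | 27 ± 1 | 30 ± 2 | 33 | 54" and the hours as "In Hours Post Dose 1 | 624 ± 12 | 696 ± 48 | 768 | 1272". Its AE row is "Adverse Events | | | X | X". The Concomitant Medications row is also empty at the first two visits, and SAP Table A.1-6 repeats both rows.
- **PK visits.** Sections 7.4.10 and 7.4.11 give the same single purpose for the 24 ± 12 h and 96 ± 48 h visits: "Subject to return to clinic to obtain serum and urine samples for PK".
- **Dose 12 visit.** Section 7.4.9 lists AE and concomitant-medication review before dosing. After dosing it lists an examination, vital signs and oximetry within 2 h, then "Spirometry at 20, and 60 minutes, 4 hours post dose", PK blood to 8 h and sweat chloride. It lists no AE review. Table A.1-5 marks the day ("Adverse Events | X | | X | | X") without saying whether this means before or after dosing.
- **Elicitation rule.** Section 12.4.2 states: "A consistent methodology of non-directive questioning for eliciting AEs at all subject evaluation time points should be adopted". Both of its example questions ask about the time since the previous visit.
- **Endpoint.** Section 4.1.1 makes the primary endpoint "Incidence and severity of adverse events (AEs) from baseline through end of study", together with the occurrence of DLTs over the same period.

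**The concern.** AE incidence and severity are primary, and dose 12 is the point of largest cumulative exposure. Solicited questioning nevertheless stops there for a week, while the subject is seen three times: until 8 h after dosing, at about 24 h, and at about 96 h. Events in those days are first asked about by recall at Day 33.

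Three things would be at stake:

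- **Quality of AE data.** Mild or short-lived events, their onset dates and the medicines taken for them are what recall captures least reliably. Medicines matter because the DLT definition in Section 4.4 turns on whether intervention was needed.
- **Comparability over time.** AE questioning is spaced differently after dose 12 than during treatment, so a late or cumulative pattern is harder to interpret.
- **Speed.** SAP Section 2.5.2 wants Grade 2 or higher AEs of interest passed to the DSMC without waiting for the cohort to finish. Under Section 4.3 a single such event triggers expansion of the cohort.

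**Working it through.** **Inputs.** Days with an AE review in the MAD cohorts from Day 1 on (Protocol Tables A.1-2 to A.1-6): 1, 3, 4, 5, 8, 10, 12, 15, 17, 19, 22, 24, 26, 33, 54. Dosing days: 1, 3, 5, 8, 10, 12, 15, 17, 19, 22, 24, 26. Dose 12 is at 600 h and the End of Treatment visit at 768 h. All visits are assumed attended.

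**1. The plan's own interval.** 33 − 26 = 7 days. In hours, 768 − 600 = 168 h, and 168 / 24 = 7.0 days. The two agree.

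**2. Gap after each dose**, from the dosing day to the next later day with an AE review:

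| Dose | 1 | 2 | 3 | 4 | 5 | 6 | 7 | 8 | 9 | 10 | 11 | 12 |
|---|---|---|---|---|---|---|---|---|---|---|---|---|
| Days | 2 | 1 | 3 | 2 | 2 | 3 | 2 | 2 | 3 | 2 | 2 | 7 |

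The maximum for doses 1 to 11 is 3 days (72 h). Dose 3 also has a same-day post-dose AE review. If that is counted, the maximum is still 3 days, from doses 6 and 9.

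**3. Ratio.** 168 / 72 = 2.3 on Monday-Wednesday-Friday dosing. Section 7.1 allows up to 4 days between doses, which gives 168 / 96 = 1.75.

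**4. Favourable reading of Table A.1-5.** If the AE mark on Day 26 is taken to extend to the last timed contact, 8 h after dosing, the gap is 168 − 8 = 160 h. That still exceeds 96 h.

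**5. Post-dose lists compared.** Doses 1, 2, 3, 4, 7 and 10 have post-dose assessments that include an AE review (Sections 7.4.3, 7.4.4, 7.4.6, 7.4.7). Doses 5, 6, 8, 9 and 11 have no post-dose items at all (Section 7.4.8). Dose 12 is the only dose with listed post-dose assessments but no AE review among them.

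**6. What the Day 33 question reaches.** The second PK visit falls 48 to 144 h after dose 12. A question limited to the time since the last clinic visit then looks back 168 − 144 = 24 h to 168 − 48 = 120 h, that is, 1 to 5 days. Taken literally, it leaves the first 2 to 6 days after dose 12 unasked.

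**7. DLT window.** Section 4.5 counts MAD DLTs within the first 4 weeks. Read as ending about Day 28, this window contains the 24 h visit (Day 27), and the next AE review (Day 33) comes about 5 days after it closes.

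**8. After the change.** With reviews at nominal Days 27 and 30, the gaps are 27 − 26 = 1, 30 − 27 = 3 and 33 − 30 = 3 days. At the extremes of the visit windows the longest gap would be 144 − 12 = 132 h, still below 168 h. With 32 planned MAD subjects, the change touches up to 32 × 2 = 64 PK visits.

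**The case against.** A reader might infer that the primary AE and DLT endpoint is least well ascertained after the last dose. The documents do not support that:

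- **Collection is continuous.** Section 8.1 captures AEs throughout the study, and Section 12.4.1 collects them to at least 30 days after the last dose, or to the start of new therapy if earlier. Spontaneous reports between visits count.
- **Escalation waits.** Under Section 4.3 the DSMC decides only after the End of Treatment visit, so the Day 33 review is in hand.
- **DLTs are acute, treated events.** Section 4.4 requires medical intervention, and such events are unlikely to be lost within a week.
- **Other doses are watched less on the day.** Dose 12 has an examination, vital signs, oximetry, spirometry to 4 h and blood draws to 8 h. Doses 5, 6, 8, 9 and 11 have no listed post-dose assessment.
- **The longest gap lies elsewhere.** Day 33 to Day 54 is 54 − 33 = 21 days.

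All of this stands and limits the point to solicited, timely reporting.

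It can also be argued that a PK-only visit is not an evaluation time point. Section 4.2 does distinguish returning for sampling from being evaluated at 7 and 28 days. On that reading Section 12.4.2 is not breached at the PK visits. If they are evaluation time points, questioning is already required and only the table needs aligning. Either way, the examination and spirometry after dose 12 are plainly evaluations, and no AE review is listed with them.

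Finally, the 96 h visit may fall as late as 144 h, where it adds little. The 64 visits are opportunities to ask, not missed events.

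**Conclusion.** The point holds as a schedule weakness. After dose 12 the next listed AE and concomitant-medication review is 7 days away, against at most 3 days after any earlier dose on Monday-Wednesday-Friday dosing and 4 days at the longest permitted interval (a ratio of 2.3 or 1.75). This sits poorly with Section 12.4.2, and that section's example questions do not clearly reach back over the whole week.

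The likely loss is in prompt solicited reporting of mild or transient events, in onset dates, and in medicines used. It is not a loss of coverage of treated DLTs, and no AE period goes uncollected. How many events would be missed or misdated cannot be derived, because the documents give no recall or reporting rate. The conclusion assumes full attendance and sites that follow the listed procedures. A site that already asks about AEs at the PK visits would close the gap in practice. The change is worth making because it is cheap and serves the primary endpoint.

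**What to change.** 1. In Protocol Table A.1-6 and SAP Table A.1-6, mark the Adverse Events and Concomitant Medications rows at the 24 h and 96 h visits.
2. Add AE review and concomitant-medication review to Sections 7.4.10 and 7.4.11 and to the post-dose list of Section 7.4.9.

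**Cost.** Two sets of table cells and three short additions to the protocol text. In conduct, a few minutes of questioning at visits that already take place, with no new visit or sample, and slightly more AE data entry.

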APPENDIX 2: SCHEDULE OF LABORATORY TESTS

Table A.2-1: Single Ascending Dose Cohorts 1-4

| Labs | Screening | Check-In | Dose | | | Discharge | | | End of Study ^a | |
|----------------------------------------------------------------|-----------------------------------------------------------------------------------------------------------------------------------------------------------------------------------------------------------------------------------------------------------------------------------------------------------------------------------------------------------------|----------------|----------------|----|----|----------------|----|-----|---------------------------|----------------|
| Study Day | ≤-14 days ^b | -1 | 1 | 2 | 3 | 4 | 5 | 6 | 7 | 8 |
| In Hours | | -24 | 0 | 24 | 48 | 72 | 96 | 120 | 144 | 168 |
| Hematology | X | X | X | X | X | X | | | | X |
| Serum Chemistry | X | X | X | X | X | X | | | | X |
| Hematology & Chemistry | Day 1: Pre-dose, 30, 60 minutes, 2, 4, 8, 12 hours post dose | | | | | | | | | |
| C-Reactive Protein | | X | X | X | | | | | | X |
| Erythrocyte Sedimentation Rate | | X | X | X | | | | | | X |
| C-Reactive Protein & Erythrocyte Sedimentation Rate | Day -1 Day 1: Pre-dose, 24 hours post dose | | | | | | | | | |
| Coagulation and CH50 | X | | | | | | | | | X |
| Direct Antiglobulin Test | X | | | | | | | | | X |
| Serum Tocopherol (Vit. E) | X | | | | | | | | | |
| Urine microalbumin | | X | | | | | | | | X |
| Urinalysis | X | X | X | X | X | X | | | | X |
| | Day 1: On pooled PK samples Day 2, 3, 4, 8: Random sample, preferably 1 st morning void | | | | | | | | | |
| Drug Screen | X ^c | | | | | | | | | |
| Pregnancy test ^d | X | X | | | | | | | | X |
| Sputum for Microbiology | | X | | | | | | | | X |
| CFTR Genotyping ^e | X | | | | | | | | | |
| CFTR Sequencing | | X ^f | | | | | | | | |
| Sweat Chloride | X | | | | | | | | | |
| PK Sampling | Serum: 0, 0.5, 1, 2, 3, 4, 12, 24, 48, 54, 72, 168 hours post dose Urine: Pre-dose; Pooled from 0 to 4, 4 to 12, and 12 to 24 hours post-dose; and 48, 72, and 168 hours post dose (UA on each pooled sample). Sputum: 3 samples obtained within first 6 hours post dose; 24 hours post dose; Day 4 (72 hours post dose); and Day 8 (168 hours post dose) | | | | | | | | | |
| Serum for PK | | | X | X | X | X | | | | X |
| Urine for PK | | | X | X | X | X | | | | X |
| Sputum for PK | | | X ^g | X | | X ^h | | | | X ^g |

| Labs | Screening | Check-In | Dose | | | Discharge | | | | End of Study^a |
|-----------------------------------------|------------------|-----------------|-------------|---|--|------------------|--|--|--|---------------------------------|
| Biomarker Sampling | | | | | | | | | | |
| Blood (serum and plasma) for Biomarkers | X | X ^g | | X | | X | | | | X |
| Sputum for Biomarkers | X | X ^g | | X | | X | | | | X |

^a For subjects who withdraw prematurely from the study, this visit will occur whenever they leave the study.

^b The screening period for an individual subject may be extended for an additional 7 days at the discretion of the Sponsor's Medical Monitor. See Section 7.2 for details.

^c Drug screening may be performed on urine or blood sample.

^d Women of child-bearing potential only

^e Required if original documentation for CF genotyping is not available or is earlier than the year 2000.

^f Samples may be collected on Day 1 pre-dose instead of Day -1.

^g Suggest obtaining samples in conjunction with performing spirometry at 10, 60 minutes, and 4 hours post dose.

^h Sample may be taken any time prior to discharge (Day 4) or during visit (End of Study).

Table A.2-2: Multiple Ascending Dose Cohorts 5-8, WEEK 1

Dosing Schedule assumes Monday-Wednesday-Friday dosing:

| Study Procedures | Screening | | Dose 1 | Dose 2 | | Dose 3 | | |
|----------------------------------------------------------------|-----------------------------------------------------------------------------------------------------------------------------------------------------------------------------------------------------------------------------------------------------------------------------------------------------------------------------------------------------------------------------|----------------|----------------|--------|----|--------|-----|-----|
| Study Day | ≤-14 days ^a | -1 | 1 | 3 | 4 | 5 | 6 | 7 |
| In Hours | | -24 | 0 | 48 | 72 | 96 | 120 | 144 |
| Hematology | X | X | X | X | X | | | |
| Serum Chemistry | X | X | X | X | X | | | |
| Hematology & Chemistry | Dose 1: Pre-dose, 30, 60 minutes, 2, 4, 8, 12 hours post Dose 1 Dose 2: 60 minutes and 4 hours post Dose 2 | | | | | | | |
| C-Reactive Protein | | X | X | | | | | |
| Erythrocyte Sedimentation Rate | | X | X | | | | | |
| C-Reactive Protein & Erythrocyte Sedimentation Rate | Day -1 Day 1: Pre-dose | | | | | | | |
| Coagulation and CH50 | X | | | | | | | |
| Direct Antiglobulin Test | X | | | | | | | |
| Serum Tocopherol (Vit. E) | X | | | | | | | |
| Urine microalbumin | | X | | | | | | |
| Urinalysis | X | X | X | X | X | | | |
| | Dose 1: Pre-dose, 0-4, 4-12 hours post dose (UA on each pooled sample) Dose 2: 60 minutes and 4 hours post dose | | | | | | | |
| Drug Screen | X ^b | | | | | | | |
| Pregnancy Test ^c | X | X | | | | | | |
| Sputum for Microbiology | | X | | | | | | |
| CFTR Genotyping ^d | X | | | | | | | |
| CFTR Sequencing | | X ^e | | | | | | |
| Sweat Chloride | X | | | | | | | |
| PK Sampling | Serum: 0, 0.5, 1, 2, 3, 4, 12; pre-Dose 2; 2 hours post Dose 2; 72 hours post Dose 1; 96 hours post Dose 1 (pre-Dose 3) Urine: Pre-dose; Pooled from 0 to 4 and 4 to 12 hours post Dose 1 (UA on each pooled sample). A separate sample should be collected at 72 hours post Dose 1. Sputum: 3 samples obtained within first 6 hours post Dose 1 and Day 4 (72 hours) | | | | | | | |
| Serum for PK | | | X | X | X | X | | |
| Urine for PK | | | X | | X | | | |
| Sputum for PK | | | X ^f | | X | | | |
| Biomarker Sampling | | | | | | | | |
| Blood (serum and plasma) for Biomarkers | X | X ^e | | | X | | | |
| Sputum for Biomarkers | X | X ^e | | | X | | | |

- ^a The screening period for an individual subject may be extended for an additional 7 days at the discretion of the Sponsor's Medical Monitor. See Section 7.2 for details.
- ^b Drug screening may be performed on urine or blood sample.
- ^c Women of child-bearing potential only.
- ^d Required if original documentation for CF genotyping is not available or is earlier than the year 2000.
- ^e Samples may be collected on Day 1 pre-dose instead of Day -1. Samples for CFTR sequencing should not be collected for subjects who participated in SAD cohort.
- ^f Suggest obtaining samples in conjunction with performing spirometry at 10, 60 minutes, and 4 hours post dose.

Table A.2-3: Multiple Ascending Dose Cohorts 5-8, WEEK 2

| Labs | Dose 4 | | Dose 5 | | Dose 6 | | |
|-----------------------------------------------------------------------|------------------------------------------------------------------------|------------|---------------|------------|---------------|------------|------------|
| Study Day | 8 | 9 | 10 | 11 | 12 | 13 | 14 |
| In Hours | 168 | 192 | 216 | 240 | 264 | 288 | 312 |
| Hematology | X | | | | | | |
| Serum Chemistry | X | | | | | | |
| Hematology & Chemistry | Dose 4: Pre-dose, 15, 60 minutes, 2 hours post dose | | | | | | |
| C-Reactive Protein | X | | | | | | |
| Erythrocyte Sedimentation Rate | X | | | | | | |
| C-Reactive Protein & Erythrocyte Sedimentation Rate | Dose 4: Pre-dose | | | | | | |
| Coagulation and CH50 | X | | | | | | |
| Urinalysis | X | | | | | | |
| | Dose 4: Pre-dose, 60 minutes and 2 hours post dose | | | | | | |
| PK Sampling | Serum: Prior to Dose 4, 5, and 6 Sputum: Prior to Doses 4, 5, and 6 | | | | | | |
| Serum for PK | X | | X | | X | | |
| Sputum for PK | X | | X | | X | | |
| Biomarker Sampling | Dose 4: Pre-dose | | | | | | |
| Blood (serum and plasma) for Biomarkers | X | | | | | | |
| Sputum for Biomarkers | X | | | | | | |

Table A.2-4: Multiple Ascending Dose Cohorts 5-8, WEEK 3

| Study Procedures | Dose 7 | | Dose 8 | | Dose 9 | | |
|-----------------------------------------------------------------------|-------------------------------------------------------------------------|------------|---------------|------------|---------------|------------|------------|
| Study Day | 15 | 16 | 17 | 18 | 19 | 20 | 21 |
| In Hours | 336 | 360 | 384 | 408 | 432 | 456 | 480 |
| Hematology | X | | | | | | |
| Serum Chemistry | X | | | | | | |
| Hematology & Chemistry | Dose 7: Pre-dose, 15, 60 minutes, 2 hours post dose | | | | | | |
| C-Reactive Protein | X | | | | | | |
| Erythrocyte Sedimentation Rate | X | | | | | | |
| C-Reactive Protein & Erythrocyte Sedimentation Rate | Dose 7: Pre-dose | | | | | | |
| Urinalysis | X | | | | | | |
| | Dose 7: Pre-dose, 60 minutes and 2 hours post dose | | | | | | |
| PK Sampling | Serum: Prior to Dose 7, and 1 hours post Dose 7; Prior to Doses 8 and 9 | | | | | | |
| Serum for PK | X | | X | | X | | |
| Biomarker Sampling | Dose 7: Predose | | | | | | |
| Blood (serum and plasma) for Biomarkers | X | | | | | | |
| Sputum for Biomarkers | X | | | | | | |

Table A.2-5: Multiple Ascending Dose Cohorts 5-8, WEEK 4

| Study Procedures | Dose 10 | | Dose 11 | | Dose 12 |
|----------------------------------------------------------------|-----------------------------------------------------------------------------------------------------------------|------------|------------|------------|------------|
| Study Day | 22 | 23 | 24 | 25 | 26 |
| In Hours | 504 | 528 | 552 | 576 | 600 |
| Hematology | X | | | | |
| Serum Chemistry | X | | | | |
| Hematology & Chemistry | Dose 10: Pre-dose, 15, 60 minutes, 2 hours post dose | | | | |
| C-Reactive Protein | X | | | | |
| Erythrocyte Sedimentation Rate | X | | | | |
| C-Reactive Protein & Erythrocyte Sedimentation Rate | Dose 10: Pre-dose | | | | |
| Urine microalbumin | X | | | | |
| Urinalysis | Dose 10: Urine microalbumin pre-dose Dose 10: Urinalysis pre-dose, 60 minutes and 2 hours post dose | | | | |
| Sweat Chloride | | | | | X |
| PK Sampling | Serum: Pre-Dose 10 and 11; Dose 12 (pre-dose; post dose at 1, 2, 3, 4, 8 hours) Urine: Dose 12 pre-dose only | | | | |
| Serum for PK | X | | X | | X |
| Urine for PK | | | | | X |
| Biomarker Sampling | Dose 10: Pre-dose | | | | |
| Blood (serum and plasma) for Biomarkers | X | | | | |
| Sputum for Biomarkers | X | | | | |

Table A.2-6: Multiple Ascending Dose Cohorts 5-8, Follow-up

| Study Procedures | PK Follow-up 24 hours After Last Dose | PK Follow-up 96 Hours After Last Dose | 7 Days After Last Dose (End of Treatment) ^a | 28 Days After Last Dose (End of Study) ^a |
|-----------------------------------------|------------------------------------------------------------------------------------------------------------------------------------------------------------------------------------|---------------------------------------------|-----------------------------------------------------------------|-----------------------------------------------------------|
| Study Day | 27 | 30 | 33 | 54 |
| In Hours Post Dose 1 | 624 ± 12 | 696 ± 96 | 768 | 1272 |
| Hematology | | | X | X |
| Serum Chemistry | | | X | X |
| C-Reactive Protein | | | X | |
| Erythrocyte Sedimentation Rate | | | X | |
| Coagulation and CH50 | | | X | |
| Direct Antibody Test | | | X | |
| Urine microalbumin | | | | X |
| Urinalysis | | | X | X |
| Pregnancy test ^b | | | X | X |
| Sputum for Microbiology | | | X | |
| Sweat Chloride | | | X | X |
| PK Sampling | Serum post last dose: 24 ±12 hrs, 96 ± 48, hours post last dose, and at End of Treatment and End of Study Visit Urine post last dose: 24 ±12 hrs, 96 ± 48, hours post last dose | | | |
| Serum for PK | X | X | X | X |
| Urine for PK | X | X | | |
| Biomarker Sampling | End of Treatment and End of Study Visits | | | |
| Blood (serum and plasma) for Biomarkers | | | X | X |
| Sputum for Biomarkers | | | X | X |

^a See Section 5.5.2 for details on these visits for subjects who withdraw prematurely from the study.

^b Women of child-bearing potential only

